#### **5.1.3. Additional assessments**

As a sub-analysis, qualitative outcomes will be collected and measured with patients, providers, and leaders. These outcomes will be collected and evaluated, per a forthcoming sub-study protocol addendum. Patient details will be identified and pulled from the EMR retrospectively after their completion of the study. Historical health records may be pulled to explore baseline rates of risk factors among prior behavioral health patients at CHS.

#### **5.1.4. Adverse Events**

Safety/Serious Adverse Events that will be specifically monitored/evaluated include suicide ideation and death. Suicide ideation is tracked among the intervention population at each touch

point. Death rates can be compared between the usual care and intervention populations once a month using data in the Enterprise Data Warehouse. Death is noted based on notification to CHS by a friend or family member or from identification of death from the social security death index which occurs through monthly updates.

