### **4. SUBJECT AND SITE SELECTION**

#### **4.1. Accrual**

As part of current care, patients are identified by an ED physician in the ED as needing psychiatric evaluation, and a referral is made to the telepsychiatric provider for a virtual consult. Patients are eligible to be included in analysis for the project if they meet the inclusion/exclusion criteria and the telepsychiatric consultation occurs during potential BH – VPN hours. We will accrue patient data for evaluation during a period starting in June 2017. Based on data from 2016, we estimate 500 patients will complete a telepsychiatric consult in a 6-month period during potential BH-VPN hours of operation. Patients will not be accrued on days where the navigators could not potentially be available, such as nights, weekends, and holidays.

Once a patient is in the intervention arm, the patient remains in the intervention arm until 45 days, or if there is a failure to contact (4 phone calls in 12 days), if the patient becomes enrolled with a case management program, declines services, or if the patient dies. After 45 days, a patient is eligible to be re-enrolled in either arm of the study.

A patient remains in the control arm for 45 days unless the patient returns to the ED on a day where patients are being randomized to the intervention arm.

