## **5.2. Randomization and Allocation**

Randomization for the purposes of this project, will be based on days the Navigators are available to treat patients who've completed their telepsychiatric consult per the BH-VPN or usual care. Patients may be in the ED for multiple days. Their enrollment status depends on the day and time of their initial telepsychiatric consultation. Navigation will only be available for those patients whose consult occurs during intervention day/times. As part of the research design and rollout of this project, randomization will occur at the day level with the days being identified as intervention or usual care days for the duration of the study. We expect an average of 3.7 patients seen daily for both hospitals combined. Patients will accrue in both arms of the study Monday through Friday during the hours of operation. Patients will not be accrued on days where the navigators are not available such as weekends, nights, and holidays.

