#### **5.4. Follow-up**

Patients being treated on the BH-VPN will receive a follow-up phone call within 24 to 72 hours from discharge, and then weekly for up to 45 days. A follow-up assessment is completed upon each phone call.

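### The only between-arm safety comparison, deaths, relies partly on family reports, while scheduled calls are described in one arm only: a risk of earlier, and possibly more complete, detection under navigation.

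*Combined protocol and SAP*

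**What the plan says.** Section 5.1.4 of the protocol names two safety events, suicide ideation and death. Ideation is tracked in the intervention population only, so death is the one safety event with a between-arm comparison. The wording is permissive: "Death rates can be compared between the usual care and intervention populations once a month using data in the Enterprise Data Warehouse".

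The same section gives two routes by which a death becomes known. One depends on somebody telling the health system: "Death is noted based on notification to CHS by a friend or family member". The other does not: "identification of death from the social security death index which occurs through monthly updates".

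Scheduled contact is described for one arm. Under section 5.4, patients on the navigation pathway "will receive a follow-up phone call within 24 to 72 hours from discharge, and then weekly for up to 45 days". Section 5.2 limits the service: "Navigation will only be available for those patients whose consult occurs during intervention day/times". For the other arm, section 4.1 says "A patient remains in the control arm for 45 days", subject to a return to the ED on an intervention day. That sets time in the arm and describes no contact. Section 5.5 marks failure to connect as an end reason for the intervention arm only, and lists death as a separate end reason.

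Not every intervention-arm patient is called. Section 4.4 excludes direct admissions and patients with neurocognitive disabilities from the service. Section 5.3 lets patients decline. Sections 4.1 and 5.5 end contact after failed calls or enrolment in another care management program.

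**The concern.** Two arms are to be compared on an event whose detection may depend partly on contact that only one of them is scheduled to receive. A weekly caller can learn of a death from a relative before the next index update. A death outside the health system in usual care has no comparable scheduled prompt. Sections 5.1.4 and 6 do not restrict the comparison to one source, set a common look-back or allow for index lag.

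Section 10 sends deaths to a data and safety monitoring board, and section 11 lets the study end if the board finds it unsafe. Uneven ascertainment could produce an apparent excess under navigation when mortality is equal. It could also lead a real excess to be put down to better detection. Sections 10 and 10.1 both describe the population as high risk, so the comparison should be readable.

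**Working it through.** **Arm size.** Section 6.1 uses 50% versus 35%, 85% power and alpha 0.05; section 6.2 makes tests two-sided. The continuity-corrected two-proportion formula gives 207 per arm, 414 in total, which matches the plan. The design effect is 1 + (2 − 1) × 0.1 = 1.1, and 414 × 1.1 = 455.4, which matches the stated 456. That is 228 per arm. This sets the scale only; the point does not depend on it.

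**Share of the intervention arm that could be called.** I use the design admission rates as a stand-in for patients admitted and so not called. At 50% admitted, 228 × 0.50 = 114 (50%). At 35% admitted, 228 × 0.65 ≈ 148 (65%). These are upper limits, before neurocognitive exclusions, refusals and lost contacts.

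**Detection model.** The documents give no mortality, index capture or family-report rates, so these inputs are assumptions:
- s = share of deaths in the index by the time of the look: 0.8, 0.5 or 0.3
- family report = 0.2 for a patient not called, 0.8 for a patient called
- p = share of intervention-arm deaths in called patients: 0.50 or 0.65 (deaths assumed proportional to patients)
- the two sources are independent, and deaths learned on calls reach the data used for the comparison

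Arm-level family report under navigation is r = 0.8p + 0.2(1 − p), which is 0.50 at p = 0.50 and 0.59 at p = 0.65. In usual care r = 0.20. The share of deaths detected is 1 − (1 − s)(1 − r).

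| s | Usual care | Navigation, p = 0.50 | Navigation, p = 0.65 | Ratio at equal mortality |
|---|---|---|---|---|
| 0.8 | 1 − 0.2 × 0.80 = 0.840 | 1 − 0.2 × 0.50 = 0.900 | 1 − 0.2 × 0.41 = 0.918 | 1.07 to 1.09 |
| 0.5 | 1 − 0.5 × 0.80 = 0.600 | 1 − 0.5 × 0.50 = 0.750 | 1 − 0.5 × 0.41 = 0.795 | 1.25 to 1.33 |
| 0.3 | 1 − 0.7 × 0.80 = 0.440 | 1 − 0.7 × 0.50 = 0.650 | 1 − 0.7 × 0.41 = 0.713 | 1.48 to 1.62 |

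At s = 1 both arms detect every death and the ratio is 1.00.

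**Second parameterisation.** Let f be unsolicited family report in both arms and c the extra capture by calls. Usual care detects 1 − (1 − s)(1 − f), and navigation detects 1 − (1 − s)(1 − f)(1 − pc). At the mild end (s = 0.9, f = 0.5, c = 0.5, p = 0.5): 0.9625 / 0.95 = 1.01. At the strong end (s = 0.5, f = 0.2, c = 0.9, p = 0.65): 0.834 / 0.60 = 1.39. The direction is the same and the size depends on the inputs.

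**Timing alone.** The mean wait to the next weekly call is 7/2 = 3.5 days. To the next monthly update it is 30/2 = 15 days. Both ignore reporting delay.

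**Number of deaths.** At an assumed 45-day mortality of 0.2% to 1%, 228 × 0.002 ≈ 0.5 and 228 × 0.01 ≈ 2.3 deaths are expected per arm.

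**The case against.** A reader might infer that deaths will be found both sooner and more often under navigation, that the comparison is biased, and that the board cannot read it. The documents do not support that.

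- The index is not limited to one arm and needs no study contact. If it is eventually complete, final counts agree and only deaths since the last update are affected. Its completeness is not stated.
- Treating the whole arm as called (p = 1, r = 0.8) would give 0.96/0.84 = 1.14, 0.90/0.60 = 1.50 and 0.86/0.44 = 1.95. Sections 4.4 and 5.3 rule that out.
- The mechanism is inferred. No section says navigators ask relatives about vital status. A patient who has died may be closed as unreachable after four calls in 12 days (section 4.1). Navigator data are held in HealtheCare (section 6), and no section says that deaths learned there enter the Enterprise Data Warehouse.
- No test, threshold or stopping rule is tied to the comparison. Section 10 also weighs events against expected population rates, and section 10.1 refers to a separate monitoring plan, not included here, that may deal with sources.
- With so few deaths, the comparison would say little even with perfect ascertainment.

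All of this stands as a limit on size and certainty. It does not remove the point. The looks are monthly, so timing matters at each one. Weighing against expected rates does not help if completeness differs by arm. Whether navigator-learned deaths are counted is itself left unspecified.

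**Conclusion.** The point holds as a risk of differential ascertainment. At the monthly looks, deaths in the intervention arm may be detected earlier, and possibly more completely, than in usual care. A lasting difference in counts is not established; it would need an incomplete index and call-learned deaths that reach the compared data.

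The ratios in the table, from about 1.07 to 1.62, rest wholly on assumed capture rates and on deaths falling in proportion to patients called. They would be lower after refusals and lost contacts. The practical weight comes from the small number of deaths: one found in only one arm could change how the board reads the comparison. Primary and secondary outcomes, which come from encounter records, are not affected. This is a cheap improvement to the safety section, not a flaw in the main analysis.

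**What to change.** In section 5.1.4:

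1. Base the between-arm death comparison on deaths found by matching every enrolled patient in both arms, called or not, to the same social security death index update.
2. Count by date of death within a fixed window from index ED discharge, for example 45 and 90 days. Section 4.4 lists death as a possible ED disposition, so say how a death before ED discharge is counted. Section 4.1 allows re-enrolment, so say to which arm a death belongs when a patient has entered more than once.
3. Flag the source of each death. Give the board, as supplementary information, the all-source count by arm and a list of deaths learned from calls or families, so that no known death is hidden.

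The cost is a few sentences, the index match and a source flag in the monthly query. The downside is that the comparative count lags by the index update and is limited by the completeness of the index. The all-source list covers that gap for individual review.

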## **5.2. Randomization and Allocation**

Randomization for the purposes of this project, will be based on days the Navigators are available to treat patients who've completed their telepsychiatric consult per the BH-VPN or usual care. Patients may be in the ED for multiple days. Their enrollment status depends on the day and time of their initial telepsychiatric consultation. Navigation will only be available for those patients whose consult occurs during intervention day/times. As part of the research design and rollout of this project, randomization will occur at the day level with the days being identified as intervention or usual care days for the duration of the study. We expect an average of 3.7 patients seen daily for both hospitals combined. Patients will accrue in both arms of the study Monday through Friday during the hours of operation. Patients will not be accrued on days where the navigators are not available such as weekends, nights, and holidays.

## **5.3. Behavioral Health Virtual Patient Navigation (BH-VPN)**

The BH-VPN outlines the flow of patients from initial contact to their follow-up calls (see Appendix 1). In the existing ED workflow patients are identified by an ED physician in the ED as in a behavioral health crisis and needing psychiatric evaluation. A referral is made to the telepsychiatric provider for a virtual consult performed on a tablet in the ED. Once the consultation is completed, the patient is placed either in usual care (the control) or BH-VPN (the intervention arm of the study). The placement is dependent upon the day and hours of the week, as to whether navigation is available. After virtual consultation is performed via tablet, the telepsychiatrist will recommend to the ED provider that the patient either be admitted or discharged from the ED, ultimately that decision lies with ED provider. If the patient in the intervention arm does not have neurocognitive disabilities such as Alzheimer's and discharge is recommended, the patient will be approached by the virtual navigator. The patient has the option not to be followed by the navigator. The navigator will complete the initial virtual behavioral health assessment. The initial health assessment contains information such as preferred communication method, primary care provider, psychiatry provider, collateral resources, recent ED and hospital utilization, substance use disorder, medication barriers, appointment barriers, community resources, and crisis planning.

The follow-up assessments, which will occur during navigation phone calls every at least weekly includes information such as a suicide ideation safety screening, an appointment reminder, appointment barrier evaluations, medication obtainment follow-up, substance use disorder follow-up, supportive listening, psychoeducation, community resource follow-up, and additional crisis planning.

The Columbia-Suicide Severity Rating Scale (C-SSRS) helps identify whether someone is at risk for suicide, and the severity and immediacy of the risk. It also identifies level of support the person needs. The screening tool is administered during each phone contact to measure suicide ideation. If a patient is deemed actively suicidal then the navigator will recommend transfer to mobile crisis, calling 911 for a well-check, or 911 to go to the ED as per current standard of care.

#### **5.4. Follow-up**

Patients being treated on the BH-VPN will receive a follow-up phone call within 24 to 72 hours from discharge, and then weekly for up to 45 days. A follow-up assessment is completed upon each phone call.

#### **5.5. Patient Completion of Participation**

Patients who are treated per the protocol on the control or intervention arm will complete their participation after 45 days or if one of the following occurs:

- Unable to connect: calls attempted over 12 days (intervention arm only)
- Death
- Enrolled in another Care Management program (intervention arm only)
- Declined services
- 45 days post-discharge completed

A patient's utilization may be tracked post 45 days after completion.

#### **5.6. Continuation of the Intervention**

Participating ED sites may continue treating patients with the BH-VPN after the study period has ended.

### **6. DATA COLLECTION AND REPORTING**

Patient demographics, comorbid conditions, and utilization will be obtained from the electronic medical record and billing systems. Data from the initial assessment and follow-up contacts will be stored in HealtheCare, a care management platform in Cerner. Data will be retrieved by an application specialist on the research team. Data may be retrieved retrospective to a patient's completion of the intervention or usual care arm of the study. A monthly executive summary will be produced, showing patient volume, percent patients with suicidal ideation, and utilization.

## 6.1. Sample size analysis and statistical analysis

We are conducting the study for about 6 months leading to approximately 6 months\*4 weeks\*5 days=120 days with 60 days allocated to intervention and 60 allocated to treatment as usual. This study is designed to detect a 15% absolute reduction in the inpatient admission within 5 days of index ED presentation with the usual care group assumed to have a 50% inpatient admission rate (internal report). We will have 85% power to detect this reduction with a total sample size of 414 ( $\alpha=0.05$ ) using a Chi-square test for independence. We will not need to adjust for attrition as the primary outcome of inpatient admission <5 days is obtainable from electronic health records for all individuals. To account for the possible correlation among patients seen in the ED on the same day, we have inflated the sample size by 10% assuming the average number of patients per ED per day is 2 and the intra-class correlation coefficient=0.1 (Design effect=1+(2-1)ICC). Therefore, our target sample size is N=456.

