Study Procedures	Patients who present to the ED at one of the two participating CHS EDs with a telepsychiatric consult performed will be treated and followed per the proposed CHS behavioral health patient navigation pathway (BH-VPN) or usual care. As part of the current care process, Patients are identified by the ED physician in the ED as needing psychiatric evaluation and a referral is made to the telepsychiatric consult, the care of these patients will follow the allocated BH-VPN pathway or

	
usual care. Regardless of participation in the BH-VPN pathway or usual care, the ED providers decide based on available information the ultimate disposition for patients --discharge from the ED or admit to the hospital.
 
Patients who complete a telepsychiatric consult in the ED Monday through Friday during the hours of operation can be enrolled to either the control or intervention arm based on a randomization scheme that randomly allocates days that navigators are available. On days where the navigator is available, all patients who meet eligibility criteria will be considered exposed to the interventions; whereas, on days the navigator is not available all patients will be considered exposed to Usual care. Patients who are in the intervention arm will be offered navigation services for 45 days following ED discharge.
 
The BH-VPN pathway is defined by several key components:
 
 
• Introduction of the navigation process to the patient, while in the ED
 
• Evaluation of the patient and their needs.
 
• Follow-up evaluation within 72 hours by phone, and weekly contact with the BH-VPN until 45 days post ED discharge
 
• Confirm that a follow-up visit is scheduled and if the patient made it to the appointment.
 
• Placement into an appropriate case management program, if needed
 

Statistical Analysis
	
Analyses will include all patients identified as having completed telepsychiatric consult and meeting the additional inclusion and exclusion criteria. Comparisons of the intervention and usual care groups will be made using univariate analyses such as the t-test and chi-square test. The primary outcome, ED to inpatient conversion, will be compared between the two groups of patients using logistic regression. Results will be presented with odds ratios and 95% confidence intervals.

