## 6.2. Statistical analysis

All analyses will follow intention to treat such that patients will be analyzed based on the allocated intervention on the day of their ED visit (BH-VPN or treatment as usual). We will compare the two groups on age, sex, suicide ideation, and neurocognitive disorders to assess for balance, which is inferred with randomization.

The primary outcome, inpatient admission  $\leq 5$  days, will be compared between the two groups of patients using a chi-square test. We will explore differences by site by conducting stratified analysis by hospital. We will attempt to adjust for the correlation among patients seen on the same day using a generalized linear mixed model with a log link and random effect for day, nested within hospital. If convergence problems arise due to small sample sizes, we will collapse by week rather than day. We will also control for hospital as a fixed effect in the model. Results for group comparisons will be presented with odds ratios and 95% confidence intervals.

Secondary outcomes are 45-day post discharge utilization (yes/no), 90-day post discharge utilization (yes/no), QCC defined 30-day readmission (yes/no), and patient centric 30-day readmission (yes/no). Each of the secondary outcomes are dichotomous and will be compared using the same approach as the primary outcome. All tests will be two sided and the data will be analyzed using SAS Enterprise Guide version 6.1. For all outcomes, we assume if there are no visits in the CHS electronic medical record that the value for having a visit is null; therefore, there will be no missing data for the primary or secondary outcome measures.

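### Section 6.1 computes the design effect for one ED-day (2 patients), but the randomised unit is the day across both EDs (3.7 patients), so 85% power at N=456 rests on an unstated near-independence of the two EDs

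*Combined protocol and SAP*

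**What the plan says.** Three places describe days as the unit of allocation. The Study Procedures entry of the Protocol Summary refers to a "randomization scheme that randomly allocates days that navigators are available". Section 5.2 says that "randomization will occur at the day level with the days being identified as intervention or usual care days for the duration of the study". Section 6.1 counts a single pool of about 120 days, with "60 days allocated to intervention and 60 allocated to treatment as usual". On volume, Section 5.2 states: "We expect an average of 3.7 patients seen daily for both hospitals combined".

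The sample size in Section 6.1 is for 50% versus 35%: "We will have 85% power to detect this reduction with a total sample size of 414". It is then enlarged by 10%. The stated reason is "To account for the possible correlation among patients seen in the ED on the same day", and the calculation is made "assuming the average number of patients per ED per day is 2 and the intra-class correlation coefficient=0.1 (Design effect=1+(2-1)ICC". The result is N=456.

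Section 6.2 says the primary outcome "will be compared between the two groups of patients using a chi-square test". It adds that the team will try to adjust for same-day correlation with a mixed model whose random effect is day nested within hospital, and with hospital as a fixed effect.

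**The concern.** When whole days are allocated, the design effect must count every patient who shares an allocated day. Here that is about 3.7 patients in two EDs. Section 6.1 counts only the 2 in one ED, and the random effect in Section 6.2 makes the same choice. Both therefore set the correlation between patients at different EDs on the same day to zero. Nothing in the document states or supports this.

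The value could lie on either side of what the plan can tolerate. Section 2 describes a telepsychiatry service shared across EDs, which makes a positive correlation plausible. Section 5.3 leaves the final disposition to the ED provider, which makes a value below the within-ED 0.1 plausible.

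If the correlation is positive, two things follow. The analyses planned in Section 6.2 understate the variance and reject too often under the null. An analysis that does respect the randomised day keeps 5%, but may not reach the stated 85% power. A reader of Section 6.1 cannot see that dependence.

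**Working it through.** **Inputs.** From Section 6.1: 50% versus 35%, alpha 0.05, 85% power, ICC 0.1, 2 patients per ED per day, N=456. From Section 6.2: two-sided tests. From Section 5.2: 3.7 patients per day, so 3.7/2 = 1.85 per ED if volumes are equal (assumption). From Section 4.1: 500 patients expected in 6 months. The between-ED same-day correlation, rb, is not given; it is assumed over 0 to 0.10. The upper end means no ED-specific day effect at all.

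**The plan's figures.** With p̄ = 0.425 and d = 0.15, the uncorrected size per arm is n = [1.96·√(2·0.425·0.575) + 1.036·√(0.25+0.2275)]² / 0.15² = 193.5, or 388 in total. With continuity correction, n' = (n/4)·[1+√(1+4/(n·d))]² = 206.6, so 207 per arm and 414 in total. The plan's 414 thus matches the corrected formula. Then 414 × 1.10 = 455.4, so 456. Both figures reproduce. Also 456/120 = 3.8 patients per day, which fits one day-schedule covering both EDs.

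**Design effect for the randomised day.** DE = 1 + (1.85−1)·0.1 + 1.85·rb. At rb = 0.10 this is 1 + (3.7−1)·0.1 = 1.27.

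**Power at N=456.** Per arm, n' = 456/(2·DE). Uncorrected power is Φ[(0.15·√n' − 1.96·0.6991)/0.6910]. Corrected power replaces n' by (n' − 1/0.15)²/n'. At DE 1.27, n' = 179.5. Uncorrected: (2.010−1.370)/0.691 = 0.926, or 82.3%. Corrected: the equivalent n is 166.4, giving 79.3%.

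| rb | DE | effective N | power, corrected | power, uncorrected |
|---|---|---|---|---|
| 0 | 1.085 | 420.3 | 85.6% | 87.8% |
| 0.01 | 1.1035 | 413.2 | 85.0% | 87.2% |
| 0.05 | 1.1775 | 387.3 | 82.5% | 85.0% |
| 0.10 | 1.27 | 359.1 | 79.3% | 82.3% |

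At rb = 0.10, keeping 85% would take 414 × 1.27 = 526 patients (388 × 1.27 = 493 uncorrected).

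**Largest rb that keeps 85%.** Corrected: (456/413.2 − 1.085)/1.85 = 0.010. Uncorrected: (456/386.9 − 1.085)/1.85 = 0.051. With the plan's 2 per ED the limits are 0.002 and 0.039.

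**If 500 accrue over 120 days** (4.17 per day, 2.083 per ED), power corrected/uncorrected is 88.1%/89.9% at rb = 0, 84.9%/87.2% at 0.05 and 81.7%/84.3% at 0.10. The 85% then holds up to rb of 0.049 or 0.088.

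**Type I error.** For the unadjusted chi-square it is 2·[1−Φ(1.96/√DE)]. For a model that adjusts for the ED-day only, DE is replaced by DE/1.085.

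| rb | chi-square | ED-day model |
|---|---|---|
| 0 | 6.0% | 5.0% |
| 0.05 | 7.1% | 6.0% |
| 0.10 | 8.2% | 7.0% |

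**Simulation check** (20,000 runs, 124 days, two EDs, 456 patients, cluster-robust tests without continuity correction). Type I error for unadjusted, ED-day and day clustering was 7.4%, 5.8% and 5.0% at rb = 0.05, and 8.8%, 6.9% and 5.2% at rb = 0.10. Rejection under 50% versus 35% at rb = 0.10 was 87.5%, 85.3% and 81.5%. The unadjusted test keeps its rejection rate only by giving up the 5% level.

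**The case against.** The strongest reply is that Section 6.1 contains no miscalculation. The ED-day cluster is stated openly and agrees with Section 6.2. At zero between-ED correlation the plan slightly exceeds its target. The shortfall depends on a parameter that the documents do not give, and the 0.10 end is an extreme. This stands: the finding is an unjustified assumption about the cluster, and its cost can only be shown as a range.

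It can also be said that the limit of 0.01 comes from a continuity correction that the plan never names and that a mixed model would not use. For that analysis the uncorrected column is the relevant one: the limit is about 0.05 and the low end is 82.3%. That is fair, and both columns are shown because 414 reproduces only with the correction.

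The ICC of 0.1 is itself unsourced. If a single smaller ICC covered the whole 3.7-patient day, 85% would hold up to (456/413.2 − 1)/2.7 = 0.038 corrected, or (456/386.9 − 1)/2.7 = 0.066 uncorrected. The limits on rb therefore hold only for a within-ED ICC of 0.1.

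The expected 500 patients would recover most of the power, but would not repair type I error. The chi-square's 6.0% at rb = 0 comes from ignoring clustering altogether, not from the choice of ED-day over day; the excess specific to this point is the 5.0% to 7.0% of the ED-day model.

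Finally, the protocol never says outright that one schedule serves both EDs. The day-level allocation, the 60/60 split of 120 days and 456/120 = 3.8 all point that way, and no separate schedules are described.

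**Conclusion.** The concern holds. The cluster used in Sections 6.1 and 6.2 is smaller than the unit randomised in Section 5.2, and the independence between EDs that this requires is neither stated nor justified. The mismatch is clear from the text; the size of its effect is conditional and modest. Over assumed between-ED correlations of 0 to 0.10, power at N=456 runs from about 86% down to 79% corrected, or 88% down to 82% uncorrected, and the ED-day model's type I error runs from 5% to 7%. These figures assume a within-ED ICC of 0.1, equal volumes at the two EDs, constant cluster sizes and one day-schedule for both sites. It should be fixed, chiefly because neither planned analysis fully accounts for the randomised day if that correlation is positive.

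**What to change.** In Section 6.1, compute the design effect for the randomised day (3.7 patients, both EDs). Give power at N=456 as a range over assumed between-ED correlations of 0.10 to 0: about 79% to 86% corrected, or 82% to 88% uncorrected. Say which formula was used. State that one schedule covers both EDs; if each ED has its own, say that instead, since the ED-day would then be the right cluster.

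In Section 6.2, make the random effect (or cluster) the calendar day shared by both EDs and keep hospital as a fixed effect. Base the primary inference on that adjusted analysis, with the chi-square as descriptive or supportive.

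The cost is text in two sections. No extra patients or data are needed. The power statement becomes conditional and slightly less favourable, and confidence intervals will be somewhat wider if the between-ED correlation is positive.
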